8.6	Audits and inspections	43
8.7	Collection and Reporting of Adverse Events/Adverse Drug Reactions	43
9.	REFERENCE LIST	43

LIST OF ABBREVIATIONS AND DEFINITION OF TERMS

The following abbreviations and special terms are used in this study Clinical Study Protocol.

Abbreviation or special term	Explanation
AE	Adverse event
COPD	Chronic obstructive pulmonary disease
CRF	Case Report Form
CSR	Clinical Study Report
EC	Ethics Committee, synonymous to Institutional Review Board (IRB) and Independent Ethics Committee (IEC)
GCP	Good Clinical Practice
ICH	International Conference on Harmonisation
ICS	Inhaled corticosteroid
ICF	Informed Consent Form
LABA	Long-acting beta2 agonist
LAMA	Long-acting muscarinic antagonist
LSLV	Last Subject Last Visit
OAE	Other Significant Adverse Event
QIP	Quality Improvement Program

Abbreviation or special term	Explanation
QS	Quality Standards
QCI	Quality Control Indicators (QCI)
PI	Principal Investigator
RA	Research Agreement
RSI	Reference Safety Information – reference information for the expectedness of a serious adverse reaction to the IP
SABA	Short-acting beta2 agonist
SAMA	Short-acting muscarinic antagonist
SAE	Serious adverse event

QIP LEXICON OF KEY TERMS

The Quality Improvement Program will be innovative in its development of a central set of “Quality Standards” for COPD care, and in its approach to characterising target patient groups and their clinical management. For consistency in the use of clinical and programme language across the programme, an agreed lexicon of key terms has been summarised below.

Term	Definition
Quality Improvement Programme	The purpose of the Quality Improvement Programme is to improve the management of COPD patients especially those with high exacerbation risk, and to support the adoption of guideline-led clinical decision-making for all COPD patients, with a focus on assessment, therapy, and follow-up of patients with modifiable high-risk COPD.
QIP Cluster Randomised Controlled Trial	The impact of The Quality Improvement Program on COPD outcomes will be evaluated in the subset of patients by a cluster-randomised controlled trial (CRT); tier 2 OR tier 3 level hospitals across China will be the cluster units of randomisation.
COPD exacerbation (EMR database definition)	A significant worsening in respiratory symptoms in people with COPD. Either a moderate exacerbation defined as use of systemic corticosteroids and/or antibiotics for at least 3 days; or a severe exacerbation that is an inpatient COPD-related hospitalization or COPD-related death. Exacerbations occurring a minimum of 7 days apart or more will be considered as separate exacerbations.
Diagnosed COPD patient with high exacerbation risk	Patients with COPD who have had 2 or more moderate, or 1 or more severe exacerbations in the last 12 months, AND whose medical record data indicates clearly that there is scope for management optimisation. Patients with frequent exacerbations are at higher future risk of exacerbations. Frequent exacerbations are linked to accelerated lung function decline, greater risk of cardiovascular events and death, and larger healthcare costs. Guidelines state that frequent exacerbators should have their treatment optimised to reduce the risk of future exacerbations and potentially other adverse events. QIP aims to address the management needs of such patients by promoting improved treatment and follow-up.

Patients with scope for management optimisation	High-risk patients who continue to have exacerbations whilst on their current therapy. The intervention will focus on patients whose management may be optimised by correct diagnosis, or where current therapy allows for the addition of at least one inhaled therapy in accordance with GOLD 2022 strategy or national guidelines or where non-pharmacological interventions can be improved.
Quality Standards	The “Chinese Quality Standards of COPD clinical care” (known as the Quality Standards or QS) have been agreed by a panel of 18 experts in COPD, informed by national COPD guideline. There are four evidence-based Quality Standards encompassing identification, clinical assessment, pharmacological and non-pharmacological intervention, and patient follow-up.
Collation of PRO/PRI questionnaire data	At least every 3 months bringing together of PRO/PRI data received during the implementation of the intervention to be used in data analysis and feedback.

RESPONSIBLE PARTIES

Name	Professional title	Role in study	Affiliation	Email address
[name]	Professor of Respiratory Medicine	Primary investigator	Shenzhen People's Hospital	[contact]
[name]	Professor of Respiratory Medicine	Sub-investigator	Shenzhen People's Hospital	[contact]
[name]	PhD of Respiratory Medicine	Sub-investigator	Guangzhou Institute of Respiratory Diseases	[contact]
[name]	PhD of Respiratory Medicine	Statistician	Shenzhen People's Hospital	[contact]

PROTOCOL SYNOPSIS

A Prospective, multicentre, cluster-randomised controlled trial to evaluate the impact on the implementation of COPD quality standards in exacerbation risk patients

----- **A COPD Quality Improvement Program (QIP)**

Background and Rationale

Chronic obstructive pulmonary disease (COPD) is currently the most common chronic respiratory disease in China which causes a huge economic and social burden. Acute Exacerbation is a crucial issue that cannot be ignored in the management of COPD. Patients with frequent exacerbations have been found to have greater airflow limitation, a greater symptom burden, increased mortality, and worsen the quality of life (QoL). However, The COPD management of those patients in clinical practice is poor in China. Patients with a low standard of care, lack of regularly pharmacological and non-pharmacological intervention, and insufficient follow-up and disease education in clinical practice.

Objectives and Outcomes

QIP(Quality Improvement Programme) is a COPD quality improvement program in China. The initial step of this program is to set up the Quality Standards(QS) of COPD management in clinical practice, then embed Quality Standards into routine care and uses Quality Control Indicators (QCI)to check the QS implementation. The aim of the QIP program is to standardize COPD management in clinical practice in China, including the standardization of diagnosis, assessment, pharmacological and non-pharmacological intervention, and follow-up. COPD patients can benefit from standardization clinical behaviours, to be identified early, be

accessed comprehensively, and be treated correctly according to guidelines, and with an appropriate follow-up to improve adherence.

The objective of QIP study is to address key gaps in management of patients with high-risk through a targeted quality improvement programme in a healthcare system or practice. The aim is to evaluate the impact of QS implementation on target population compared to usual care in a real-world setting, including but not limited to COPD exacerbation, lung function, quality of life, and treatment pattern.

Primary Objective	Outcome Measure
To evaluate the effectiveness of QS implementation on clinically important deterioration (CID)	Time to CID, which is defined as the time from the date of enrolment until the date of the first CID. CID defined as any of the following events: 
1) Trough FEV₁ decline $\geq 100\text{ml}$2) CAT increasing ≥ 2 unit3) one moderate or severe exacerbation
Secondary Objective:	Outcome Measure:
To evaluate the impact of QS implementation on exacerbations, lung function and symptoms in COPD patients	
• Annual rate of moderate or severe COPD exacerbation• Annual rate of severe COPD exacerbation• Change from baseline in trough FEV₁ over 48 weeks• Change from baseline in CAT over 48 weeks

To describe COPD management and treatment adherence in QS implementation group and usual care group	
• Proportion of patients received inhalation technique review at least once during follow-up period• Proportion of patients received long-acting inhaled medicine with percentage of days covered (PDC) $\geq 80\%$ over 48 weeks
To describe intervention group and control group on treatment pattern in stable COPD	
• Proportion of prescription of inhaled maintenance medicine at 12, 24, 36, 48 weeks .• Proportion of patients prescribed ICS-containing inhaled maintenance medicine at 12, 24, 36, 48 weeks .

Study design

This is a interventional, cluster-randomized, pragmatic clinical study. A total of 41 hospitals will be selected. Among them, 40 eligible hospitals will be selected across China and randomized (stratified by tier and geographic region) to the intervention group or control group at the ratio of 1:1. In addition, the leading site will be assigned to the intervention group without following the randomization procedure. In the intervention group, QS implementation will be performed. The control group will maintain the current practice. Eligible patients will be recruited in both groups and will be followed up every 12 weeks for 48 weeks.

Study population

The target populations in this study are the diagnosed COPD patients with exacerbation history. Age ≥ 40 years, at least 2 moderate or 1 severe exacerbation in the previous year; or 1 moderate exacerbation in the previous year with $FEV1 < 50\%$ predicted value at baseline;.

Those patients currently are symptomatic(CAT ≥ 10),or have progressive worsening of airflow restriction, and with a scope of optimization in COPD management as judged by physicians.

Intervention

The intervention was delivered at the hospital level. The intervention group will receive QS implementation, including QS training for physicians of respiratory department every 12 weeks; QS implementation check every 12 weeks, and follow-up every 12 weeks, QS-related written COPD clinical procedures will be also suggested to established key QS training requirements are:1) COPD diagnosis and assessment; 2)Therapy prescribed in accordance with national guideline 3)Non-pharmacological interventions; 4)An appropriate follow-up according to QS.

The control group will maintain current practice and follow up every 12 weeks.

Data Sources

The Electronic Data Capture (EDC) system will be used for data collection and query handling. Participating patients will be followed up for at least 48 weeks for data collection. This will include data from the EMR, medical charts, and other sources in healthcare centres in the intervention group and control group. The CAT score will be collected through questionnaire. Patient questionnaire will be collected in CRF by a study staff who will not be involved in recruitment and training.

Assuring Allocated Regimens are Implemented

Unlike traditional clinical trials where there is a near perfect guarantee of the application of the allocated treatment, this real-world cluster-randomized trial may face some barriers in the allocated exposure being applied in hospitals, especially since the intervention is a clinical pathway change. To measure the effective implementation of the intervention, the Quality Control Indicators(QCI) will be regular checked by each site PI who is responsible for the QS implementation of their department.

Statistical methods

Sample Size

A total of 1107 patients will be enrolled in the study(41 clusters, 27 patients in each cluster). With 40(20 per treatment group) clusters randomized at a 1:1 ratio (Intervention group: control group) and a size of 27 individuals per cluster (21 after drop out, assuming 20% drop out), approximately 1080 patients will be enrolled from the 40 randomized hospitals. In addition, the leading site will be assigned to the intervention group without following the randomization procedure and approximately 27 individuals will be enrolled. Whilst, data from the leading site will be excluded from the primary analysis set.

If the true hazard ratio (HR) for the comparison of QS versus Usual Care group in this patient population is 0.70, assuming ICC is 0.079 (ICC of 0.079 was estimated using analysis of variance method based on results from a pilot study¹⁰), 713 CID events will provide 80% power to demonstrate a statistically significant difference in CID free duration at a 5% 2-sided significance level (this could translate to an increase of median time to CID from 121 days to 172 days), assuming CID free duration is exponentially distributed.

Methods for statistical analyses

Descriptive statistics will be calculated, including n, means, standard deviations, medians, and interquartile ranges for continuous variables and frequency counts and percentages for categorical variables. Percentage will be calculated based on non-missing data unless otherwise specified. Data will be examined for skewness, outliers, and systematic missing data. Transformations will be undertaken as needed. All statistical procedures will be conducted using SAS version 9.4 or later, while graphs may also be produced using R.

The primary outcome measure is time to CID. The primary outcome analysis will be based on FAS, which includes all enrolled subjects among all randomized hospitals who had at least one post-baseline efficacy data assessments. Comparison between treatment groups will be

conducted using a clustered log-rank test at two-sided significance level of 0.05. Kaplan-Meier curve of time to CID will also be presented by treatment group.

Except for comparison of primary outcome measure, all other comparisons will be exploratory while nominal p value might be provided if applicable. Changes from baseline in trough FEV1, CAT over 48 weeks will be analysed using a random effects model. Rate of moderate or severe COPD exacerbation and rate of severe exacerbation will be analysed using random effects Poisson regression. The endpoints of proportion of patients received inhalation technique review at least once during follow-up period, proportion of patients received long-acting inhaled medicine with percentage of days covered (PDC) $\geq 80\%$ over 48 weeks, proportion of prescription of inhaled maintenance medicine at each visit, and proportion of patients prescribed COPD-related medicine at each visit will be summarised. Descriptive statistics for these endpoints will be presented by treatment group.

Sensitivity analysis will be conducted among all enrolled subjects who had at least one post-baseline efficacy data assessments.

INTRODUCTION

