3.2.2.1 Translating the Quality Standards into practice

The intended pathway and interlinking of the Quality Standards during implementation of the QS is shown in Figure 2. Different hospitals may differ, however, to translate the Quality Standards into practice the following requirements must be adhered to. Where acceptable, options to modify these components to suit each hospital needs are provided.

a) QS 1:Assessment of disease and quantification of future risk

Eligible patients following the QS 1 assessment process goes on to have a thorough clinical assessment to characterise their disease status. This clinical assessment will also consider the patient's risk of future exacerbations, cardiac events and mortality.

Assessment of disease

- **Symptom assessment** to be performed during follow-up period.
 - The COPD Assessment Test (CAT) (Jones et al. 2009, Jones et al. 2012) score (Appendix 2)(developed to quantify symptom burden in COPD using a concise and simple set of questions) is the core symptom assessment method in the QS. It is referred to frequently in COPD guidelines and is used to help guide treatment.
 - Symptom assessment should be performed at least every 12weeks, but may be performed more frequently depending on frequency of patient review and disease stability.

- **Exacerbation Risk** Number and severity of exacerbations since previous review to be recorded in EMR.

Quantification of future risk

- **Comorbidities** including osteoporosis, diabetes mellitus, gastroesophageal reflux disease (GERD), anxiety and depression to be actively sought and managed.
- **Risk prediction** QS will be used to quantify risk of future events and/or mortality. Details regarding specific risk score methods used should be documented and available for sharing with the QC team where possible.
 - Information resulting from risk assessment to be conveyed to patient when felt to be beneficial by healthcare provider.

b) **QS 2: Pharmacological and non-pharmacological interventions**

Following thorough assessment, QS 2 focuses on ensuring patients receive therapy and intervention in line with their risk and clinical parameters. The focus in QS 2 is to identify opportunities to increase or alter treatment such that health outcomes are improved. The following list of pharmacological and non-pharmacological interventions are core components of the QS and should be routinely applied.

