- **Initial therapy for newly diagnosed** patients to be based on China COPD guideline classification and recommendations
- **Modification of therapy** for high-risk patients to be made in accordance with current China COPD guideline follow-up pharmacological treatment algorithms, utilizing information obtained during assessment. The focus is on inhaled maintenance therapy, other COPD therapies to be evaluated in accordance with China COPD guideline.
- **Smoking cessation intervention(s)** such as referral to smoking cessation services and prescription of pharmacotherapy for smoking cessation to be offered at initial assessment and subsequent review as required.

- **Pulmonary rehabilitation** according to need and physician's recommendation.
- **Vaccination** pneumococcal and influenza vaccines will be recommended.

c) **QS 3: Appropriate follow-up**

COPD is a chronic disease and effort to optimise management must continue beyond initial assessment or diagnosis in the provision of regular multi-faceted follow-up consultations.

- **Medication and symptom review** must involve the recording of current therapy, medication adherence, exacerbation history since previous review and current symptoms.
- **Inhaler technique** to be reviewed at least once during study period and corrections in technique made as necessary.
- **Spirometry** performed for monitoring purposes and to detect those with rapid decline in FEV1 (defined as more than 40ml per year (Vestbo J et al. 2011)).

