3.2.2.2 Quality Control (QC) team

Implementation of QS requires input from some clinical staffs of participating hospitals.

The QC team members are recommended to be directors of respiratory departments from participating hospitals and should familiarise themselves with the Quality Standards and core QS components(Figure 2).

The QC team responsibilities include:

- Coordination of overall delivery of the QS
- Facilitate understanding of the overall project objectives and rationale
- Ensure the site-level delivery of QS education and training
- Assess the site-level QS implementation and quality
- Collect feedback of physicians from respiratory departments from participating hospitals

- Regular check implementation performance and review implementation process. This may be achieved by a sub-group in the team who are responsible for ongoing assessment of the programme, and for making recommendations for modifications where necessary.

The QS training will be performed every 3 months by the QC team, the initial one will be a comprehensive face-to-face training and with a full test before sites launch. And the training content of next 3 times during study period will be determined based on the assessment and feedback of implementation sites.

The control group will maintain their usual care. COPD usual care is decided by the physician based on the clinical practice.

Patients in both groups will be trained of exacerbation identification.

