5.4 Bias

5.4.1 Methods to Minimise Bias

Potential sources of bias come from differences between hospitals, which includes participation in different tiers and different geographic regions, differences in the capability of COPD management exist between the same tier hospital in different cities. There may be a selection bias that occurs because the hospitals need to meet the inclusion criteria in order to participate in the study. However, clustered randomization, with every attempt to balance the

hospital tiers and geographic regions within each group, will somewhat equalize these medical centers across both study groups, to mitigate this bias. Additionally, an extra backup hospital will be selected in each strata to minimize selection bias. If a hospital withdraw from the study after randomization, the backup hospital in the corresponding strata will replace it.

Periodic collection of relevant data in the control group will improve the compliance of patients, to a certain extent, that will affect the HCP's attention to patients.

However, an independent team (a nurse from each site who will not be involved in recruitment and training) will be supposed to collect data in both groups to reduce and to balance the influence between data collection and the purpose for the study.

Potential cross-contamination across groups from patients transfer to different hospitals. In order to reduce contamination, the QIP study will choose 8 hospitals in each region. Hospitals will be selected from five regions of the whole country, namely, east, west, north, south and central. In addition, it will be emphasized in ICF and try to encourage patients to seek care at the study hospital if they need.

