6.2 Procedure

6.2.1 Enrolment period

At Visit 0, patients who met all of the inclusion criteria and none of the exclusion criteria will be enrolled. At this visit, as showing in table 1, the investigator will obtain baseline data, including demographics, medical/surgical history, COPD exacerbation history in the previous

year, smoking status, COPD-related medication, comorbidities, clinical laboratory tests, physical examination etc.

The patients' latest spirometry data before visit 0 and the spirometry data obtained at Visit 0 should be confirmed for the inclusion criterion. If the previous spirometry data is not available, the pulmonary function test should be performed first. Re-screening is not allowed for patients who do not meet the spirometry criteria at Visit 0.

6.2.2 follow-up period

Patients will return to the study hospital every 12 weeks for the on-site visit.

During on-site visits, in the intervention group, patients should be reassessed for the attainment of treatment goals and identification of any barriers to successful treatment. Following a review of the patient's response to treatment initiation, adjustments in pharmacological treatment may be needed. The following content needs to be strengthened during this period:

- Review of symptoms(CAT score) and Exacerbations.
- Assess the inhaler technique and adherence and non-pharmacological interventions.
- Adjust the inhaler device and pharmacological interventions.
- Smoke cession education and COPD disease education.

During on-site visits, in the control group, there is just data collection every 12 weeks according to the study plan as showing in table 1.

The purpose of the Patient Questionnaire (Appendix 3) in this study is to confirm whether the physician review the inhaler device usage, give the patients smoke cession education and COPD-related disease education. The Patient Questionnaire should be collected at the end of every on-site visit. If the patient is unable to read the Patient Questionnaire clearly due to vision problems, the study staff should read the contents to the patient clearly but cannot explain them.

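### Exacerbations may be ascertained unequally in the two arms, because the intervention changes one of the record sources and the Protocol fixes no common method of collection

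*Protocol*

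**What the plan says.** **Endpoint.** One moderate or severe exacerbation is one of the three CID components (2.1, 4.1, 5.3.2). Exacerbations also supply two secondary annual rates (2.2).

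**Sources.** For both arms: "This will include data from the EMR, medical charts, and other sources in healthcare centres in the intervention group and control group" (synopsis, Data Sources; 3.2.4). The lexicon labels its exacerbation entry as the one for the EMR database.

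**Intervention hospitals.** QS 1 (3.2.2.1): "Number and severity of exacerbations since previous review to be recorded in EMR". QS 3 in the same section says that medication and symptom review "must involve the recording of current therapy, medication adherence, exacerbation history since previous review and current symptoms".

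**Control hospitals.** "The control group will maintain their usual care" (3.2.2.2). At their visits "there is just data collection every 12 weeks according to the study plan as showing in table 1" (6.2.2). Table 1 lists exacerbations at Visits 0 to 4 without distinguishing the arms.

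**Safeguards common to both arms.** Patients are trained to identify exacerbations (3.2.2.2). They are encouraged to return to the study hospital when they worsen, and must bring documents for care received elsewhere (6.2.2). Data are to be collected by "a nurse from each site who will not be involved in recruitment and training" (5.4.1).

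**Who collects.** Section 5.4.1 gives the task to that nurse. Section 7.2 has the investigators collect patient data and enter them in the EDC. The synopsis and 3.2.4 reserve uninvolved staff for the patient questionnaire, and none of the five items in Appendix 3 asks about exacerbations.

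**What a moderate event is.** The lexicon requires at least 3 days of systemic corticosteroids and/or antibiotics. Section 4.1.2.1 requires such treatment but sets no minimum duration.

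**The concern.** An outcome source should not depend on allocation. Here, better recording of exacerbations is part of what the intervention delivers, and the record it improves is one of the named sources for the endpoint. If a short steroid or antibiotic course is written down more reliably in intervention hospitals, that arm gains CID events and exacerbation counts with no difference in disease. The HR and the rate ratio then move toward, or past, 1.

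Timing adds to this. FEV1 and CAT are measured at the 12-weekly visits, so exacerbations are the component normally dated between visits. A missed control exacerbation delays or removes a control CID. The bias section (5.4.1) discusses differences between hospitals, the attention effect of data collection, and contamination, but not this. The sensitivity analysis in 5.3.4 differs from the primary analysis only in its population, so it would not reveal the problem.

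**Working it through.** **1. Does the text fix a common method?** Table 1 gives both arms a common schedule for exacerbations, but the row carries no note on how they are to be obtained. Sections 5.4.1 and 7.2 name different collectors. The lexicon and 4.1.2.1 give different thresholds for a moderate event. The rule on outside documents in 6.2.2 covers care at other hospitals, not uneven recording within the study hospital. Together these set when exacerbations are collected, but not one way of collecting them.

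**2. The plan's own figure.** The plan gives 713 events for 80% power at HR 0.70 with ICC 0.079. Schoenfeld's formula gives 4 × (1.96 + 0.84)² / (ln 0.70)² ≈ 247 events before clustering. The design effect is 1 + 20 × 0.079 = 2.58 for 21 patients per cluster, giving about 637 events. It is 1 + 26 × 0.079 = 3.054 for 27 per cluster, giving about 754. The stated 713 lies between and is not reproduced. That is a separate matter; below, the stated 80% is taken at face value.

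**3. Model for unequal capture.** The Protocol gives neither the exacerbation share of the CID hazard (s) nor the capture proportions, so all of these are assumptions. With proportional hazards, and the same true HR of 0.70 for every component:

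observed HR = 0.70 × (s × capture in QS arm + 1 − s) / (s × capture in control arm + 1 − s)

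| s | 95% vs 90% | 95% vs 80% |
|---|---|---|
| 0.3 | 0.70 × 0.985/0.970 = 0.711 | 0.70 × 0.985/0.940 = 0.734 |
| 0.5 | 0.70 × 0.975/0.950 = 0.718 | 0.70 × 0.975/0.900 = 0.758 |
| 0.7 | 0.70 × 0.965/0.930 = 0.726 | 0.70 × 0.965/0.860 = 0.785 |

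Equal capture returns 0.70. With no true effect, s = 0.5 and 95% vs 80%, the HR reads 0.975/0.900 = 1.08.

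**4. Power at the middle row.** The noncentrality for 80% power is 1.96 + 0.84 = 2.80.
- At 0.718: 2.80 × 0.331/0.357 = 2.60, and Φ(2.60 − 1.96) ≈ 0.74.
- At 0.758: 2.80 × 0.277/0.357 = 2.17, and Φ(2.17 − 1.96) ≈ 0.58.

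**5. Exacerbation rate ratio.** If the gap applied to every exacerbation, the ratio would be inflated by 0.95/0.90 = 1.06 or 0.95/0.80 = 1.19. It would be less to the extent that admissions are captured equally.

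**6. Dependence on the assumptions.** Let c be control capture relative to QS capture, so that the HR is 0.70/(1 − s + s × c). Then s = 0.2 and c = 0.9 gives 0.70/0.98 = 0.714, while s = 0.5 and c = 0.7 gives 0.70/0.85 = 0.824. The result runs from trivial to serious according to inputs that nobody has measured.

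**7. Why these figures are nearer upper bounds.** The formula lets the other components run at their own rates, but ignores that a missed exacerbation may itself push CAT or FEV1 over its threshold at the next visit. Such a patient still has a CID, only later.

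**The case against.** The strongest reply is that control hospitals do have a duty to collect exacerbations. Their 12-weekly visits follow Table 1, which lists exacerbations every time, and QS 1 recording covers the interval since the previous review, which in the intervention arm happens at the same 12-weekly visits. The sources include more than the EMR and charts. The efficacy definition in 4.1.2 rests on symptoms, treatment and admission, and does not mention the EMR. Concomitant medication is collected at every visit in both arms, so a moderate event should leave a treatment trail. The CRF is not shown and may already hold common questions. Appendix 3 exists to check physicians' behaviour, so its silence on exacerbations proves nothing.

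Much of this stands, and it limits both the certainty and the size of the problem. It does not remove it: a shared schedule is not a shared method, the nurse is site-based and not stated to be blinded, and the Protocol does not commit to common questions.

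A reader might infer three stronger things that the documents do not support:
- That exacerbations come only from the EMR and charts, so that capture is certainly unequal. The text adds other sources and schedules collection in both arms.
- That a real benefit is certainly hidden. Moderate events are defined by treatment given, and QS training and the quality indicators also address treatment, so the intervention may change the count itself. The net direction is not assured.
- That both exacerbation rates are equally exposed. Severe events are defined by in-patient admission, which should be on record in either arm.

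**Conclusion.** There is a real but unquantified risk of differential ascertainment, probably but not certainly toward no effect. It rests on three facts in the text: the recording duty belongs to the intervention, the record it affects is a named outcome source, and no arm-neutral method is fixed. Exposure is mainly to moderate exacerbations, which are part of one of the three CID components.

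A gap of 95% versus 90% would matter little for the HR; 95% versus 80% would matter for power. Neither capture rates nor event shares are given in the Protocol, so these figures show scale and do not predict a loss of power. The conflicts over the data collector and the moderate-event definition are plain inconsistencies whatever the size of the bias. Because correction is cheap, the change is worth making.

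**What to change.** 1. In 3.2.4 and 4.1.2, state that at Visits 1 to 4 the same independent staff role in both arms asks every patient one standard question set. It should cover worsening, steroid or antibiotic courses, and admissions since the last visit. Each reported event is confirmed against prescription, dispensing or admission records.
2. Reconcile 5.4.1 with 7.2 on who collects the data, and the lexicon with 4.1.2.1 on what counts as a moderate event.
3. Add a sensitivity analysis of time to CID that keeps the FEV1 and CAT components but counts only hospitalised exacerbations.

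There is no need to exclude EMR entries that exist because of QS 1. They could not be reliably separated from other entries.

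The cost is one CRF page at visits already held, a wording amendment and one extra analysis. The downside is a few minutes per visit and some reliance on patients' recall over 12 weeks, which confirmation against records only partly offsets.
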